10.4 DISTANCE SATURATION PRODUCT

DSP will be calculated as follows:

Parameter	Formula
DSP (m%)	= (Distance walked in meters) x (Lowest oxygen saturation recorded during the 6MWT)

Abbreviations: 6MWT, 6-Minute Walk Test; DSP, Distance Saturation Product

DSP values and associated changes from Baseline will be listed and the listing will include subject number, analysis visit, and assessment date (day). DSP values and change from Baseline values will be summarized by parent study treatment group at each analysis visit. Baseline is defined as the last DSP value obtained prior to the first dose of inhaled treprostinil in the RIN-PH-202 study.

11 SAFETY ANALYSES

11.1 ADVERSE EVENTS

AEs are captured from the time the Informed Consent Form is signed. Any AEs that are ongoing at the Study Termination Visit from study RIN-PH-201 are recorded as continuing AEs in the RIN-PH-202 study. All AEs with an onset date on or after the first dose of inhaled treprostinil in the RIN-PH-202 study or AEs ongoing from the parent study will be included in data listings and summaries.

The AEs will be coded using the Medical Dictionary for Regulatory Activities (MedDRA), and all summaries will utilize the Preferred Term (PT) and/or System Organ Class (SOC) to categorize AEs. All AEs will be organized by treatment group in the parent study and listed by subject, including onset date (day), cessation date (day), verbatim term, corresponding

SOC and PT, seriousness, date AE became serious, severity, frequency, relationship to study drug, action taken with study drug, and outcome.

The overall summary of AEs includes the number of subjects with any AE, the number of subjects with any study drug-related AEs, the number of subjects with AEs leading to study drug withdrawal, the number of subjects with AEs leading to death, the number of subjects with any serious AEs, and the number of subjects with any study drug-related serious AEs.

The summaries of AEs by SOC and PT will be provided by parent study treatment group and overall. The summaries of AEs, serious AEs, non-serious AEs, AEs probably or possibly related to inhaled treprostinil, and AEs leading to permanent discontinuation of inhaled treprostinil will include the number of subjects (percent of subjects) and number of events for each reported PT.

The total number of AEs and the AE rates will be calculated and summarized for each display, as appropriate. The AE rate will be calculated as the total number of AEs divided by the total patient years of exposure to study drug per treatment group in the parent study.

11.2 DEATHS

All deaths will be listed (including those occurring within 30 days of the last inhaled treprostinil dose for subjects who discontinued prematurely) by subject, and will include the subject number, treatment group in the parent study, date of assessment (day), date of death (day), first and last inhaled treprostinil doses in the RIN-PH-202 study, and cause of death (including other, specify text [if applicable]). A summary of deaths will be presented by the parent study treatment group and overall and will include the number (percent) of subjects who died (including those occurring within 30 days of the last inhaled treprostinil dose for subjects who discontinued prematurely) and their causes of death.

Time to death will be summarized by parent study treatment group and overall using product-limit estimates calculated by the Kaplan-Meier method and displayed graphically as Kaplan-Meier curves. A tabular summary of this analysis will include the number of subjects

at risk (sample size), estimated median duration, and a 95% confidence interval for the median duration for each parent study treatment group and overall.

In addition, a Cox proportional hazards model may be fit for time to death to obtain the hazard ratio and its associated 95% confidence interval. The model will include parent study treatment group as an explanatory variable.

11.3 HOSPITALIZATIONS DUE TO CARDIOPULMONARY INDICATIONS

All hospitalizations will be listed including admission date, discharge date, and hospitalization status at the end of the study. Those hospitalizations due to cardiopulmonary indications will be flagged. This listing will be organized by parent study treatment group.

The number and percentage of subjects who experience any hospitalizations and any hospitalizations due to cardiopulmonary indications will be summarized by parent study treatment group and overall. Additionally, the total number of hospitalizations due to cardiopulmonary indications per subject will be categorized by parent study treatment group and overall.

Kaplan-Meier analyses and Cox regression as described in Section 11.2 will also be done.

11.4 EXACERBATIONS OF UNDERLYING LUNG DISEASE

All exacerbations of underlying lung disease will be listed including start date, end date, status at the beginning and end of the study, whether the exacerbation was considered serious, and if so, the date the event became serious.

The number and percentage of subjects who experience exacerbations of underlying lung disease will be summarized by parent study treatment group and overall. Additionally, the total number of exacerbations of underlying lung disease per subject will be categorized by parent study treatment group and overall.

Kaplan-Meier analyses and Cox regression as described in Section 11.2 will also be performed.

11.5 OXYGENATION

Oxygenation is measured by pulse oximetry (SpO₂ and supplemental oxygen requirement [L/min]) during each 6MWT. At each 6MWT, pulse oximetry (for SpO₂) will be measured at pre-walk, during walk, and post-walk. During walk, the lowest SpO₂ will be recorded. All pulse oximetry results along with the collection date/time (study day) will be listed. Heart rate will be listed for pre-walk and post-walk only.

Heart rate will be summarized by parent study treatment group and overall, by time point (pre-walk and post-walk) and visit. The summary will be provided for the original values, change from pre-walk for each visit, and change from Baseline values. For change from Baseline calculations, the measurements pre-walk and post-walk at post-Baseline visits will be compared with the measurements at corresponding pre-walk and post-walk at Baseline.

11.5.1 *Pulse Oximetry*

SpO₂ will be summarized by parent study treatment group and overall at each time point (pre-walk, during walk, and post-walk) and analysis visit. The summary will be provided for the original values, change from pre-walk for each visit, and change from Baseline values. For change from Baseline calculations, the measurements pre-walk, during walk, and post-walk at post-Baseline visits will be compared with the measurements at corresponding pre-walk, during walk, and post-walk at Baseline. Baseline is defined as the last values obtained prior to the first dose of inhaled treprostinil in the RIN-PH-202 study.

In addition, for each time point at each visit, the number and percentage of subjects with SpO₂ or lowest SpO₂ <80%, ≥80% to <88%, and ≥88%, and with SpO₂ dropping ≥10% during walk and/or post-walk from pre-walk, will be summarized by parent study treatment group and overall.

11.5.2 *Supplemental Oxygen*

At each visit, supplemental oxygen requirements will be collected at rest and during 6MWT. These data will be listed, including visit, 6MWT date/time, and oxygen use at rest and during walk. The number and percentage of subjects requiring supplemental oxygen use at rest and during the 6MWT will also be summarized by parent study treatment group and overall.

Supplemental oxygen level at rest at each visit and the corresponding changes from Baseline will be summarized by parent study treatment group and overall.

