## 1.3 RATIONALE FOR DEVELOPMENT OF STUDY DRUG IN DISEASE/CONDITION

Inhaled treprostinil has shown clinical improvements in exercise capacity after 12 weeks of therapy in patients with WHO Group I PH (McLaughlin 2010). Inhaled treprostinil is expected to directly target the more ventilated portion of the lungs in patients with WHO Group 3 PH minimizing the risk of ventilation perfusion mismatch and allowing for improvements in exercise capacity (Seeger 2013).

The use of inhaled prostacyclin therapy in patients with WHO Group 3 PH has been recently evaluated. In particular, Wang and colleagues (Wang 2015) reported data on 67 COPD patients with PH and found no change in arterial blood gases when a single dose of iloprost was administered during right heart catheterization (RHC). In addition, Bajwa and colleagues recently completed a prospective 16-Week study in nine COPD subjects with PH which

reported no notable changes in arterial blood gases over the 16-Week treatment period (Bajwa submitted). Finally, Agarwal and colleagues (Agarwal 2015) recently presented data on 35 patients with WHO Group 3 PH who received treatment with inhaled treprostinil for six months. This retrospective review reported a mean increase from baseline in 6MWD of 61 meters with obstructive and restrictive patients reporting mean increases of 71 meters and 50 meters, respectively. Notably, this study also found that inhaled treprostinil was well tolerated with cough being the most commonly reported AE. Data from these recently completed pilot studies suggest that inhaled treprostinil can be safely administered in patients with WHO Group 3 PH.

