#### 3.3.2.2 Vital Signs

Vital signs will be assessed at Baseline as part of the Study Termination (Week 16) assessments from protocol RIN-PH-201 and at each subsequent study visit and at the Study Termination Visit. Vital signs measured will include blood pressure (systolic and diastolic), heart rate (HR), respiratory rate (RR), temperature, and weight. Vital signs must be assessed following at least five minutes of rest (sitting) to ensure accurate measurement. No other measurements or procedures should be performed during this five-minute period. When applicable, vital signs should be collected prior to the 6MWT. If vital signs cannot be obtained prior to the 6MWT, they should be obtained after recovery from the 6MWT. Vital signs should also be assessed in the case of abnormal clinical signs and symptoms.

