#### 3.3.2.5 Oxygenation

#### 3.3.2.5.1 Pulse Oximetry

Pulse oximetry will be assessed immediately prior to, throughout the conduct of, and immediately after each scheduled 6MWT assessment at Baseline (as part of the RIN-PH-201 Study Termination Visit), Week 4, Week 12, every 12 weeks thereafter, and at Study Termination. Pulse oximetry will include the collection of SpO2 and HR. The SpO2 and HR obtained immediately prior to and immediately following completion of the 6MWT will be recorded in the electronic case report form (eCRF). In addition, the lowest recorded SpO2 with the associated HR obtained during each 6MWT will be recorded in the eCRF.

When possible, pulse oximetry should be recorded using the provided pulse oximeter (Nonin 3150). In the event the provided pulse oximeter cannot be used (i.e., subject has known issues with obtaining accurate readings from a finger probe, etc.) an alternative device may be used with prior sponsor approval so long as the same device is used for all planned 6MWT.

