7 ANALYSIS POPULATIONS

All available data from all subjects will be used as detailed in this analysis plan.

The Safety Population will include any subject who received inhaled treprostinil at any time during the study. All analyses are based on the Safety Population.

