8.2 PREMATURE DISCONTINUATION AND MISSING DATA

A subject may voluntarily withdraw or be withdrawn from the study and/or study drug by the Investigator at any time for reasons including, but not limited to, the following:

- The subject wishes to withdraw from further participation.
- A serious or life-threatening AE occurs or the Investigator considers that it is necessary to discontinue study drug to protect the safety of the subject.
- The subject consistently deviated from the protocol.
- The subject's behavior is likely to undermine the validity of his/her results.
- The subject permanently initiates an infused prostacyclin therapy for >29 days.
- The subject becomes pregnant.

All available data from all subjects in the Safety Population, as defined in Section 7, will be used as detailed in this analysis plan.

Missing data will not be imputed.

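### A subject who attends a visit but does not attempt the walk has no planned SpO2 reading, so the by-visit percentage with low resting SpO2 may be understated

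*SAP*

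**What the plan says.** **Collection.** Protocol 3.3.2.5.1 places every scheduled reading around the walk: "Pulse oximetry will be assessed immediately prior to, throughout the conduct of, and immediately after each scheduled 6MWT assessment at Baseline" and at each later visit. SAP 11.5 matches this: at each 6MWT, SpO2 "will be measured at pre-walk, during walk, and post-walk". The visit lists in Protocol 7.2 and 7.3, including the Study Termination Visit, repeat the arrangement. SpO2 is not a vital sign. Protocol 3.3.2.2 reads "Vital signs measured will include blood pressure (systolic and diastolic), heart rate (HR), respiratory rate (RR), temperature, and weight", and SAP 11.8 carries the same items.

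**Analysis.** SAP 11.5.1 summarises SpO2 by time point and visit (Table 14.3.3.1). It then adds "In addition, for each time point at each visit, the number and percentage of subjects with" values below 80%, from 80% to below 88%, and 88% or above (Table 14.3.3.2). SAP 7 states "All analyses are based on the Safety Population" and SAP 8.2 states "Missing data will not be imputed". No denominator is given for the percentages, and there is no category or count for subjects without a reading. The summary statistics that SAP 8 lists for continuous variables do not name the number of observations.

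**What does not depend on the walk.** Protocol 3.3.2.5.2 has resting supplemental oxygen flow assessed at Baseline and scheduled visits, and SAP 11.5.2 summarises it with change from Baseline. Circumstances affecting a walk go into the 6MWT listing (SAP 10.1), but the SAP does not carry them into the SpO2 tables.

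**The concern.** Oxygenation is a safety endpoint (Protocol 2.2) and one of the main safety assessments in Protocol 3.3.2. Even the resting SpO2 value exists only as the reading before a walk. A subject who comes to the visit but does not start the walk can have laboratory tests, vital signs, adverse events and oxygen flow recorded, and still have no planned SpO2.

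Such visits are foreseeable. Follow-up runs to Week 108 in a serious lung disease, and Protocol 4.1 admits subjects who stopped parent-study drug for clinical worsening. The early Study Termination Visit, often the most informative one for a deteriorating subject, also takes SpO2 only around the walk.

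If the reason for not walking is linked to low oxygen saturation, the missing readings are informative. The study has no formal hypothesis test (Protocol 10.3), so these by-visit tables are themselves the evidence on SpO2, and they are read for trends over time. A growing share of non-walkers could keep the tabulated percentage level while resting hypoxaemia becomes more common among those attending. The question concerns subjects present at a visit; it is separate from dropout.

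**Working it through.** The documents give no figure for this point, so there is nothing of the plan's to reproduce. The check has two parts: what can be missing, and how far that could move the percentage.

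**1. Which readings can be missing.** The pre-walk value is taken before walking starts and the lowest value during the walk. Only the post-walk value is tied to completion (Protocol 3.2, footnote 8). Protocol 15.1 allows rests while the clock runs. A subject who starts and stops early can therefore still supply the first two values. All three are unplanned only when the walk is not attempted. The documents do not say whether a pre-walk reading is kept if the walk is then cancelled.

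**2. Which percentage is affected.** A non-walker has a resting saturation that could have been measured. The during-walk and post-walk values do not exist for that subject. The arithmetic below therefore applies to the pre-walk row only.

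**3. Formula.** Among subjects attending a visit, let m be the share who do not walk, and pw and pn the shares of walkers and non-walkers with low resting SpO2 (say below 88%).

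- True percentage = (1 − m) × pw + m × pn
- If the denominator is subjects with a reading, the table shows pw, and the gap is m × (pn − pw).
- If the denominator is all attending subjects and non-readings fall in no category, the table shows (1 − m) × pw, and the gap is m × pn.

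**4. Numbers.** All three inputs are assumptions. With subjects who have a reading as the denominator:

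| m | pw | pn | Shown | True | Gap (points) |
|---|---|---|---|---|---|
| 5% | 10% | 30% | 10% | 0.95 × 10% + 0.05 × 30% = 11% | 1 |
| 10% | 10% | 50% | 10% | 0.90 × 10% + 0.10 × 50% = 14% | 4 |
| 20% | 10% | 50% | 10% | 0.80 × 10% + 0.20 × 50% = 18% | 8 |
| any | 10% | 10% | 10% | 10% | 0 |

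The second and third rows also show the effect on a trend. If m rises from 10% to 20% and nothing else changes, the table stays at 10% while the true figure goes from 14% to 18%.

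**5. Wider range.** For m from 5% to 30%, pw from 10% to 30%, and pn from pw up to 60%, the gap runs from 0 to 0.30 × (60% − 10%) = 15 points. With all attending subjects as the denominator, the same ranges give 0.05 × 10% = 0.5 to 0.30 × 60% = 18 points. The unstated denominator therefore matters in itself.

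**6. Bounds that need no assumption about non-walkers.** Counting every non-reading as not low gives (1 − m) × pw; counting every one as low adds m. With pw = 10%, the bounds are 9.5% to 14.5% at m = 5%, 9% to 19% at m = 10%, and 8% to 28% at m = 20%. Each interval contains the true value in the table above.

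**The case against.** Several stronger readings are tempting, and the documents do not support them.

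- A reader might infer that SpO2 requires a completed walk. It does not: an attempted walk is enough for the pre-walk and lowest values.
- A reader might infer that the SAP restricts the summary to walkers, or that non-walkers leave the oxygenation tables altogether. The SAP names the Safety Population, and resting oxygen flow stays in Tables 14.3.3.4 and 14.3.3.5. The gap is confined to SpO2.
- A reader might infer that the bias always favours the drug. If walks are missed for reasons such as injury or logistics, pn may equal or fall below pw. With m = 10%, pw = 10% and pn = 5%, the gap is 0.10 × (5% − 10%) = −0.5 points.
- A reader might infer that the protocol names ventilation-perfusion mismatch as a risk of the drug class, with this table as its measure. Protocol 1.3 says the inhaled route is expected to reach ventilated lung, "minimizing the risk of ventilation perfusion mismatch and allowing for improvements in exercise capacity". That is a rationale for the route.

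It can also be said that deterioration is captured through adverse events, deaths, cardiopulmonary hospitalisations and exacerbations; that no test or sample size is affected; and that a count of missing readings is normally a detail of the table shells, which are not among the documents. All of this limits the weight of the point. It does not remove it: events and a flow rate do not supply a saturation and cannot correct a by-visit percentage of subjects with low SpO2. Nor can a table shell restore a reading that was never scheduled.

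**Conclusion.** The point holds as a gap in collection and reporting. Followed as written, the plan has no SpO2 reading for an attending subject whose walk is not attempted. The SpO2 category table gives the reader no denominator and no count from which to see this. The percentage with low pre-walk SpO2 in Table 14.3.3.2 may be understated, and the resting mean in Table 14.3.3.1 rests on the same incomplete set of readings.

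Understatement is the likely direction if non-walkers are more often hypoxaemic. The documents do not establish that they are. The size is wholly assumed: 1 to 8 points in the three illustrative cases, zero if walkers and non-walkers are alike. During-walk and post-walk percentages are not understated in this sense, because they describe exertion that a non-walker did not undertake. No error rate, power or sample size is involved.

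**What to change.** 1. **Protocol 3.3.2.5.1.** Record the seated resting (pre-walk) SpO2 at every scheduled visit and at the Study Termination Visit, whether or not the walk goes ahead. Use the supplied oximeter and the seated rest period already required. State that the value is kept if the walk is then cancelled.
2. **SAP 11.5.1 and Table 14.3.3.2, pre-walk time point.** Use subjects attending the visit as the denominator. Show the number with no SpO2 reading, with any recorded reason. Beside the observed percentage, give the two bounds: non-readings counted as not low, and as low.
3. **Same section, during-walk and post-walk time points.** Keep subjects who walked as the denominator and report the number who did not walk.

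The cost is one extra finger reading at visits without a walk, and a few table rows. The upper bound is conservative, so it should appear only beside the observed figure. The eCRF is not among the documents, so whether a reason is captured for every missed walk cannot be confirmed; the count and the bounds can be produced without it. The change adds an assessment and clarifies a summary; it sets no treatment rule.

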11.6 PULMONARY FUNCTION TESTS

The PFT parameters include:

- FEV₁ and percent predicted value,
- FVC and percent predicted value,
- TLC and percent predicted value, and
- DLCO for carbon monoxide and percent predicted value.

If the PFT is done both prior to and after a bronchodilator, only pre-bronchodilator values will be recorded and listed. The listing will include subject number, analysis visit, and assessment date (day) as well as each PFT result and the percent predicted values for each PFT. All PFT parameters (absolute values and percent predicted values) and their respective change from Baseline values will be summarized by parent study treatment group and overall at each visit.

11.7 CLINICAL LABORATORY TESTS

The following clinical chemistry parameters will be evaluated by the central laboratory:

Parameter	Units
Sodium	mmol/L
Potassium	mmol/L
Bicarbonate	mmol/L
Chloride	mmol/L
Total bilirubin	umol/dL
Alkaline phosphatase	U/L
Alanine aminotransferase	U/L
Aspartate aminotransferase	U/L
Urea nitrogen	mmol/dL
Creatinine	umol/L
Calcium	mmol/L
Albumin	g/L

The following hematology parameters will be evaluated by the central laboratory:

Parameter	Units
Hemoglobin	g/dL
Hematocrit	%
Red blood cell count	10 ⁶ /uL
Red blood cell morphology	
White blood cell count	10 ³ /uL
Platelet count	10 ³ /uL

Values that are “high” or “low” with respect to the reference range provided by the central laboratory will be flagged with an “H” or an “L,” respectively. All parameters will be listed for all subjects and assessments, along with their respective “high/low” flags.

Values of these parameters at each visit, and their corresponding changes from Baseline, will be descriptively summarized by parent study treatment group and overall.

For each parameter, the frequency and percentage of subjects within each parent study treatment group and overall who had “low,” “normal,” or “high” Baseline values, then subsequently had “low,” “normal,” or “high” follow-up values at each visit, will be presented in a shift summary.

Pregnancy test results for female subjects will be summarized by parent study treatment group and overall and listed by subject number, analysis visit, and pregnancy status.

